10.1.2 Primary Efficacy Analysis

Following the estimand described in [Section 10.1.1](#), the primary efficacy endpoint between CSL312 and placebo is tested for a difference by comparing the time-normalized number of HAE attacks in the 6 months of the Active Arm and in the 6-month Placebo Arm period by using a two-sided Wilcoxon Test (Hierarchical Testing H01). The monthly CSL312 dose will be evaluated against monthly placebo at alpha = 5%:

$$H_{01}: a_1 = 0 \text{ versus } H_{11}: a_1 \neq 0$$

In the above hypothesis, the term “ a_1 ” is the shift between the 2 distributions of monthly CSL312 and monthly placebo.

The time-normalized number of HAE attacks per month and per year will be summarized descriptively for the 6 months of the Active Arm and the 6-month Placebo Arm period by median and mean with corresponding 95% CIs.

Sensitivity Analysis considering baseline attack rate

As a sensitivity analysis, the time-normalized number of HAE attacks will be compared for the 6 months of the Active Arm and the 6 months of the Placebo Arm using a generalized linear model (GLM) for count data assuming a Poisson distribution with the logarithm as link function and Pearson chi-square scaling of standard errors to account for potential over dispersion. The model includes treatment (categorical) and the time-normalized baseline attack rate during Run-in Period (continuous) as covariates. To account for the length of subject treatment, the logarithm of the length of subject treatment is used as an offset variable in the model:

$$\log \lambda_i = \log(t_i) + \beta' x_i$$

where λ_i is the expected number of HAE attacks of subject i ($i = 1, \dots, n$ with n the number of subjects in ITT Analysis Set), $\log(t_i)$ is the offset with t_i as the length of the i -th subject treatment in days and x_i is the covariate of subject i which includes the time-normalized baseline attack rate of subject i and the treatment information of subject i .

From this model, the least squares mean time-normalized number of HAE attacks and the standard errors are estimated for CSL312 and placebo. The mean time-normalized number of HAE attacks ratio for CSL312 relative to the placebo and the corresponding 95% confidence interval are also estimated. To report as mean attack rate per month, the received estimates are transformed by the exponential function and scaled by time.

The mean time-normalized number of HAE attacks ratio for CSL312 relative to placebo and the corresponding 95% confidence interval estimated by the model described above will be used to calculate the percentage difference in the mean time-normalized number of HAE attacks for CSL312 from placebo as:

$$100\% * (\text{mean time-normalized number of HAE attacks ratio} - 1).$$

The 95% CI for the percentage difference will be calculated with the estimated upper and lower confidence limits for the mean time-normalized number of HAE attacks ratio, transform by subtracting 1 and multiplying by 100%.

The sensitivity analysis considering baseline attack rate will be carried out using the ITT Analysis Set.

Technical Note: the time-normalized baseline attack rate during Run-in Period (continuous) will be derived as defined in [Section 10.3.2.1](#).

Sensitivity Analysis for missing values

Missing values occur if the observation time for the treatment period is less than 30 days, i.e., a subject discontinued within 30 days after first study drug administration. Therefore, only a very low number of subjects with a missing primary endpoint are to be expected.

To assess the impact of missing data for the primary efficacy estimand a systematic approach will be applied. For each treatment arm, a range of values for the number of time-normalized HAE attacks per month from 0 to 6 subdivided into 9 increments between two consecutive integer values will be generated. All possible combinations from the subdivided ranges will be imputed to replace the missing values. For the comparison of active treatment versus placebo, observed and imputed data will be analyzed using the Wilcoxon Test and results will be classified into negative (i.e., placebo significantly better), neutral (i.e., no significant difference) and positive (i.e., active treatment significantly better).

A graph where the x-axis presents the subdivided range for placebo and the y-axis the subdivided range for the active treatment will visualize all scenarios and distinguished the different outcomes by different colors and symbols. The total number of subjects with missing outcome in placebo and active treatment arm will be added to the graph. This sensitivity analysis will only be applied to the ITT Analysis Set.

10.1.3 Supplementary Analyses of Primary Estimand

The primary estimand described above is complemented by an additional supplementary estimand and analysis.

Only subjects in the PP Analysis Set will be included. The interest is to assess the treatment effect of CSL312 during treatment from Day 1 through Day 182 while subjects are allowed to treat HAE attacks with on-demand medications but excluding subjects who do not comply with the protocol.

The additional estimand in line with the interest of the study follows the treatment policy strategy and is described as follows:

- Treatment Condition: monthly treatment of CSL312 or placebo.
- Population: the target subject population defined by eligibility criteria, who were randomized, received at least 1 dose of CSL312 and who comply with the protocol (PP).
- Variable: time-normalized number of HAE attacks per month during treatment from Day 1 through Day 182.
- Intercurrent events: The occurrence of an intercurrent event is irrelevant. All observed values will be used regardless of occurrence of any of the following intercurrent events:

- administration of on-demand medication in addition to prophylactic treatment with CSL312,
- early study discontinuation due or not due to COVID-19.
- Population-level summary: descriptive statistics of the time-normalized number of HAE attacks during treatment from Day 1 through Day 182 by treatment.

When a subject who was at least 30 days in the treatment period after the first study drug administration discontinues study treatment due or not due to COVID-19 but stays beyond the last study drug administration in the study for more than 30 days, the HAE attacks until the last study drug administration plus 30 days thereafter will be included in the supplementary analysis of the primary estimand.

If a subject has a COVID-19 infection while participating in the study, his/her attacks will be assessed during the BDRM to determine if they might be caused/triggered by other factors, e.g. COVID-19. If there is clear evidence that they are due to the COVID-19 infection or other, they might be excluded from the analyses. Missed study drug administrations not due or due to COVID-19 or COVID-19 vaccination might also lead to the exclusion of a subject or subject's data from the supplementary analysis as well as prohibited concomitant medications due or not due to COVID-19 or COVID-19 vaccination.

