4.5 Determination of the Sample Size

In total, 60 subjects are planned to be randomized.

Forty subjects with C1-INH HAE type 1 and type 2 completing the 6-month Treatment Period are needed to achieve a power of approximately 90% for a two-sided Wilcoxon Test (alpha of 5%). Subjects will be randomized to the Active Arm or the Placebo Arm with a ratio of 3:2. An attack rate per month of 0.3125 for CSL312-treated subjects and of 1.3 for subjects receiving placebo are assumed. The monthly attack rates of placebo and of CSL312 are assumed to be Poisson distributed.

The sample size calculation is performed with SAS 9.4 using proc power procedure with twosamplewilcoxon test=WMW which performs power analyses for the Wilcoxon-Test for two independent groups, i.e. the CSL312 and the Placebo treatment in Study CSL312_3001. The Wilcoxon Rank Sum test is testing from departure from the null hypothesis and is assessing if there is a location shift between the distributions of the HAE attack rates of the CSL312 and the Placebo treatment. SAS Proc Power procedure uses the O'Brien-Castelloe approach to compute approximate power. Alpha is set to 5% [O'Brien & Castelloe, 2006]. The assumed monthly attack rates of placebo and of CSL312 (i.e. 1.3 and 0.3125 attacks/month, respectively) are used as the two means of the two Poisson distributions. The randomization ratio of 3:2 was implemented by GROUPNS = (24 16) resulting in a total sample size of 40 which is the lowest one reaching 90% power.

It is targeted to randomize approximately 5 adolescents into the treatment period with a randomization ratio of 3:2 (active:placebo).

To allow for sufficient safety data, to increase the likelihood of adolescents entering the study and, to have at least 40 subjects reaching the end of the study, an additional 20 subjects are planned to be randomized.

In case it is not feasible to randomize the targeted number of adolescents, the targeted total sample size will be achieved by randomizing the needed number with adult subjects.

In addition, it is targeted to include 5 Japanese subjects into the total 60 subjects randomized.

Based on Method 1 and Method 2 in the [Basic principles on Global Clinical Trials] the sample size of the Japanese subjects are planned as below. The point estimate of the endpoint in each arm for Japanese population and other regions (for Method 2) are assumed as the same as that for the global population.

Method 1

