Generally, only data of pre-specified planned visits will be used in statistical summary analyses, and calculations of any derived parameters; data of unscheduled visits will be included in the listings only.

Actual, rather than planned, sampling time points will be used in the derivation of PK parameters and in the individual concentration-time plots and listing of PK concentration data. Planned sampling time points will be used in the descriptive summaries and in mean and median plots. Concentration-time data will be listed according to actual sampling time points relative to dosing time.

Assessment windows will not be defined for classifying measurements obtained outside scheduled assessment times.

7.1 **Coronavirus Disease 2019 (COVID-19) Impact**

As it is expected that the COVID-19 pandemic will be ongoing during the conduct of the study, the impact of COVID-19 will be assessed and reported.

Primary Estimand

The primary estimand is defined in [Section 10.1.1](#) and is taking into account intercurrent events such as:

- missed doses which might be caused by issues in the drug delivery to the patient due to COVID-19, the COVID-19 disease itself or COVID-19 vaccination scheduling/side effects (intercurrent event of non-compliance to treatment);
- early treatment or study discontinuation which might be caused by COVID-19 (intercurrent events of early treatment or study discontinuation).

Further events introduced by COVID-19 (for example concomitant medications used to treat COVID-19 or vaccinations) will be assessed in the Blind Data Review Meeting (BDRM) and might lead to an exclusion of a subject or subject's data from the PP Analysis Set which is the study analysis set defined for the supplementary analysis of the primary estimand. HAE attacks

will be also assessed during BDRM if those could be triggered by COVID-19 and decision will be made to exclude those subjects or subject's data from the PP Analysis Set.

Subject Disposition: Study Treatment Discontinuation or Study Discontinuation

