10.1 Analysis of Primary Endpoint

The primary endpoint is the time-normalized number of HAE attacks per month during the Treatment Period from Day 1 (first study drug administration) through Day 182 (inclusive).

Subjects will enter HAE symptoms into their eDiary, the start and end date and time, the interference of HAE symptom(s) with daily activities, and location(s) of the HAE symptom(s). Investigator-reported HAE attacks will be based upon review of subject diaries, relevant interval medical history, and physician judgment. The investigator may ask clarifying questions to assist in his/her assessment of whether or not an HAE attack occurred. If an attack occurred, then the investigator will record an attack in the eCRF form, the start/end date and time, the attack location(s), and the severity of the attack based on the most severe symptoms. For every visit, the investigator will report all HAE attacks that have occurred in the interim since the last visit the subject attended.

For all analyses considering HAE attacks, only the HAE attacks confirmed and reported by the investigator using the eCRF ‘HAE Attacks’ form will be used.

HAE attacks with a start date on or after the first day of the Run-in Period but prior to the date and time of the first study drug administration will be counted for the Run-in Period.

HAE attacks with a start date and time after the first study drug administration through Visit Day 182 (inclusive) or End of Study visit (whatever is first) will be counted for the Treatment Period and will be included in the analyses of efficacy.

The primary endpoint will be analyzed using the ITT and PP Analysis Set. The ITT Analysis Set will be used as the primary analysis and the PP Analysis Set will be used as the supplementary analysis (see [Section 10.1.3](#)).

The primary endpoint, time-normalized number of HAE attacks per month, is calculated per subject as:

$$[\text{the number of HAE attacks} / \text{length of subject treatment in days}] * 30.4375$$

where the length of subject treatment is calculated as:

$$[\text{the date of Study Visit Day 182 or the End of Study date [whatever is first]} - \text{the date of Study Visit Day 1 of the Treatment Period} + 1].$$

To transform the length of subject treatment which are calculated in days in years the number of days is divided by 365.25. Thus, time-normalized number of HAE attacks per year is calculated per subject as:

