10.1.1 Primary Estimand

The primary interest is to assess the treatment effect of CSL312 during treatment from Day 1 through Day 182 while subjects are allowed to treat HAE attacks with on-demand medications.

The primary estimand in line with the primary interest of the study follows the treatment policy strategy and is described as follows:

- Treatment Condition: monthly treatment of CSL312 or placebo
- Population: the target patient population defined by eligibility criteria and who were randomized (ITT).
- Variable: time-normalized number of HAE attacks per month during treatment from Day 1 through Day 182.

Intercurrent events: The occurrence of an intercurrent event is irrelevant. All observed values will be used regardless of occurrence of any of the following intercurrent events:

- administration of on-demand medication in addition to prophylactic treatment with CSL312,
- Prohibited concomitant medications due or not due to COVID-19 or COVID-19 vaccination,
- non-compliance to treatment due or not due to COVID-19 or COVID-19 vaccination,
- early study discontinuation due or not due to COVID-19.

- Population-level summary: median time-normalized number of HAE attacks per month during treatment from Day 1 through Day 182 by treatment.

If a subject discontinued the study early after being continuously the first 30 days in the treatment period, the observation is terminated by the Early Termination Visit. It is assumed that the attack rate for subjects, who discontinued the study after the 30th study day and before the end of the 6th month, is comparable to the attack rate from subjects who have the entire 6 months treatment period observed. This assumption is based on CSL312_2001 data which showed that the CSL312 treatment effect was maintained over time. Therefore, the primary endpoint will be considered measurable and not missing, ie, the time-normalized number of HAE attacks will be calculated based on the HAE attacks reported until the Early Termination Visit.

In case a subject discontinues study treatment due or not due to COVID-19 but continues participation in the study for more than 30 days beyond the last study drug administration,

the HAE attacks until the last study drug administration plus 30 days will be included in the HAE attack analysis and length of subject treatment in days will be derived as:

[date of last study drug administration – the date of Study Visit Day 1 of the Treatment Period +31].

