Missing data is only given if subjects discontinue the study within 30 days after the first study drug administration in the treatment period. An approach to handle these missing data by sensitivity analysis is described in Section 10.1.2.

During the BDRM, it will be assessed if subjects have missed subsequent study drug administrations and if this might lead to the exclusion of subject's data from the analyses. All decisions will be documented in the BDRM minutes.

A COVID-19 diagnosis and resulting intercurrent events are irrelevant for the primary estimand. All observed values will be used regardless of occurrence of any of the following COVID-19 related intercurrent events: medications given to treat COVID-19 or COVID-19 vaccinations. Non-compliance to treatment and early discontinuation will be handled the same independent if it is related to COVID-19 or not.

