10.3.3 Supplementary Analyses of Secondary Endpoints

The secondary endpoints:

- percentage reduction in the time-normalized number of HAE attacks,
- number and percentage of subjects with percentage reductions of $\geq 50\%$, $\geq 70\%$, and $\geq 90\%$,
- time-normalized number of HAE attacks per month requiring on-demand treatment,
- the time-normalized number of moderate or severe HAE attacks,

(see [Section 10.3.2.1](#), [Section 10.3.2.2](#), [Section 10.3.2.3](#)) will be further summarized separately for the first 3 months Treatment Period (Study Day 1 to Day 91), as well as the second 3 months Treatment Period (Study Day 92 to Day 182).

Supplementary Analysis of Secondary Endpoints will be conducted for ITT Analysis Set.

[figure not shown]
HAE attacks

The number and percentage of mild, moderate, and severe HAE attacks will be presented as well as the time-normalized number of mild, moderate, and severe HAE attacks during Run-in Period and Treatment Period.

[figure not shown]
A by-subject listing will show all details per HAE attack sorted by treatment arm, subject-ID and HAE Attack ID including: nominal visit, start and end date:time, anatomical location, severity, on demand treatment taken, potential trigger for this HAE attack.

An additional listing will present absolute number and time-normalized number of all, mild, moderate, and severe HAE attacks per Run-in Period and Treatment Period, duration of Run-in Period and Treatment Period as used for time-normalization for each subject.

[figure not shown]
CCI

[figure not shown]
CCI

CCI

CCI

Time to first HAE attack after Day 1 and after Day 15 during Treatment Period

Time to first HAE attack after Study Day 1 and after Study Day 15 during Treatment Period will be analyzed using the Kaplan-Meier method. Time to first HAE attack after Day 1 will be derived as:

Date of first HAE attack after Study Day 1 – Date of Study Day 1,

and Time to first HAE attack after Day 15 will be derived as:

Date of first HAE attack after Study Day 15 – [Date of Study Day 1 + 14].

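### SAP 10.1.1 lets the blinded review exclude data for missed doses although its estimand makes non-compliance irrelevant; separately, SAP 10.1.3 and 7.1 let it drop confirmed attacks from the per-protocol analysis

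*SAP*

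**What the plan says.** **Primary estimand and missed doses.** SAP 10.1.1 follows the treatment policy strategy in the ITT population: "All observed values will be used regardless of occurrence of any of the following intercurrent events". The list that follows includes non-compliance to treatment, whether or not related to COVID-19. SAP 7.1 assigns missed doses to that same event. Later in 10.1.1 the BDRM is asked to assess whether subjects missed study drug administrations and "if this might lead to the exclusion of subject's data from the analyses". Decisions go into the meeting minutes. The sentence gives no criterion and names no analysis set.

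**Which attacks count.** SAP 10.1 states that for all analyses of attacks "only the HAE attacks confirmed and reported by the investigator using the eCRF" form will be used. Follow-up time runs from the Day 1 visit to the Day 182 visit or End of Study date.

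**Attacks and COVID-19.** SAP 7.1 says attacks "will be also assessed during BDRM if those could be triggered by COVID-19", with a decision to exclude those subjects or their data from the PP set. SAP 10.1.3, on the supplementary PP estimand, has the attacks of a subject with a COVID-19 infection reviewed for COVID-19 or other causes, and adds: "If there is clear evidence that they are due to the COVID-19 infection or other, they might be excluded from the analyses". The attack listing in SAP 10.3.3 already shows the "potential trigger for this HAE attack".

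**The concern.** The missed-dose sentence matters more because it sits inside the definition of the confirmatory analysis. A treatment-policy ITT estimand keeps the data of subjects who miss doses. A clause that lets a meeting remove such data case by case replaces that estimand with one that nobody has defined, and a reader of the report could not tell in advance which subjects would be in it.

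The attack-level clause affects the supplementary analysis. The PP result is read as support for the ITT result, which is simplest when the two differ only in who is included. If single confirmed attacks can also be taken out, they differ in what counts as an event. The wording *or other* puts no limit on the causes that qualify.

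**Working it through.** **1. Missed doses: the passages side by side.**

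- SAP 10.1.1, intercurrent events: non-compliance is irrelevant and observed values are kept.
- SAP 7.1: missed doses are an instance of that event.
- SAP 10.1.1, BDRM sentence: missed administrations may lead to exclusion from the analyses.
- SAP 10.1.3, for the PP estimand: missed administrations may lead to exclusion from the supplementary analysis. The limit missing from 10.1.1 is therefore written out here.
- SAP Table 9: compliance outside 80-120% is a potential reason for exclusion from PP (and PK, PD). ITT is not named.

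The 10.1.1 sentence is not tied to the Table 9 threshold. SAP 10.6 plans 6 injections. One missed injection gives 100 x 5/6 = 83.3%, inside the range; two give 100 x 4/6 = 66.7%, outside it. Read literally, 10.1.1 lets the meeting act on either. For subjects who stop treatment but stay in the study, 10.1.1 gives a matching follow-up formula. For missed doses it gives none.

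**2. Attack removal: how far it reaches.**

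- SAP 7.1 directs COVID-19-related exclusions to the PP set.
- SAP 10.1.1 says a COVID-19 diagnosis is irrelevant for the primary estimand.
- SAP Table 9 lists a COVID-19 diagnosis under PP (SAF, PK, PD), without ITT.

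Removal is thus confined to the PP analysis, whose population-level summary in 10.1.3 is descriptive. Within that analysis it departs from SAP 10.1, which has no trigger exception. It also fits poorly with the treatment-policy label that 10.1.3 gives itself: COVID-19 infection is not among its listed intercurrent events and has no stated strategy. The follow-up formula in SAP 10.1 depends on visit dates only, so as written it does not change when an attack is removed.

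**3. Arithmetic.**

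Inputs from SAP 4.5: "An attack rate per month of 0.3125 for CSL312-treated subjects and of 1.3 for subjects receiving placebo are assumed", Poisson distributed; 24 + 16 evaluable subjects for about 90% power; 60 randomized, that is 36 and 24. From SAP 10.1: 182 days and 30.4375 days per month.

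The plan's own figure reproduces. The O'Brien-Castelloe method with 24 and 16 subjects gives 90.7% power, and a simulation of 10,000 trials gives 91.3%.

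- One attack: 30.4375/182 = 0.167 per month, in either arm.
- Expected attacks per subject: 0.3125 x 182/30.4375 = 1.87 on CSL312; 1.3 x 182/30.4375 = 7.77 on placebo.
- Expected attacks per arm: 36 x 1.87 = about 67; 24 x 7.77 = about 187.
- Planned reduction in mean rate: 100 x (1 - 0.3125/1.3) = 76.0%.

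Effect of deletions on that 76.0% (their number is an assumption; no dropout):

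| Attacks deleted | Reduction in mean rate |
|---|---|
| 5, CSL312 arm only | 77.7% |
| 5, placebo arm only | 75.3% |
| 10, CSL312 arm only | 79.5% |
| 10, placebo arm only | 74.6% |
| 1 in each of 1/9 of subjects, both arms | 77.1% |
| Same fraction of attacks, both arms | 76.0% |

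Fifth row: each arm mean falls by 0.167/9 = 0.0186, so 100 x [1 - (0.3125 - 0.0186)/(1.3 - 0.0186)] = 77.1%.

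For the primary test, simulated power with six-month counts at these rates is about 100%, at 24 + 16 and at 36 + 24 subjects.

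**The case against.** The best defence is that the SAP, read as a whole, already confines these exclusions to PP. Table 9 puts low compliance under PP, and SAP Section 7 illustrates data exclusions with PP analyses, so the phrase in 10.1.1 may simply be loose. That is probably what was meant. But the sentence stands in the primary estimand section and omits the limit that 10.1.3 states, so the text needs correcting even if the intention is sound.

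The discretion also has safeguards. PP exclusions are decided and documented before unblinding, 10.1.3 asks for clear evidence, and Protocol 10.3 foresaw excluding subjects affected by COVID-19 from some analyses. These points stand, with two limits. The protocol speaks of subjects, not single attacks. And expected counts of 1.87 and 7.77 give someone reviewing a subject's attacks a clue to the arm.

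It can also be said that cause belongs in attack assessment: Protocol Appendix 2 lets the investigator reject symptoms with a more likely alternative cause. That step, however, comes before confirmation, so the meeting would be judging cause a second time.

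Several stronger readings are tempting but unsupported:

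- **COVID-19-related attacks can be removed from the primary analysis.** SAP 7.1, 10.1.1 and Table 9 point the other way.
- **The missed-dose clause contradicts both estimands.** The PP list omits non-compliance and its population excludes non-compliers, so excluding such subjects there is consistent.
- **Only data after a missed dose would go.** The SAP refers to a subject or a subject's data.
- **7.1 and 10.1.3 set conflicting evidence thresholds.** 10.1.3 describes an assessment followed by exclusion, and the 7.1 wording matches the first step.

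**Conclusion.** The contradiction in SAP 10.1.1 is real and should be removed: the text makes missed doses irrelevant and also allows exclusion because of them. Its numerical effect cannot be stated, since the documents give no expected number of subjects with missed doses.

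The attack-level clause is a real but smaller defect, limited to a descriptive PP analysis. One deletion moves a subject's rate by 0.167 per month in either arm. Under the planning rates, full follow-up and up to 10 deletions in one arm, the reduction in mean rate stays between 74.6% and 79.5%, against 76.0%. A reader might infer that deletions favour CSL312, because 0.167 is a larger share of 0.3125 (54%) than of 1.3 (13%). The documents do not establish that: the net direction depends on where and how often deletions occur. Nor is the H01 decision likely to change, given power of about 100% on six-month counts and the confinement of attack removal to PP. The case rests on pre-specification and a consistent event definition.

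**What to change.** - **SAP 10.1.1:** delete the missed-dose sentence, or limit it explicitly to membership of the PP set, and state that no observed data are removed from the ITT primary analysis because of missed doses.
- **SAP 10.1.3 and 7.1:** restrict the BDRM to deciding whether a subject belongs to the PP set. Count every investigator-confirmed attack in the observation window for each included subject, and show triggers only in the existing listing.
- **At minimum in 10.1.3:** remove *or other* and name the supplementary analysis in place of the unspecified analyses.

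The cost is SAP wording, with no change to data collection or sample size. The downside is that a few infection-related attacks stay in the PP rate.
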